5.3.3 Maximum Tolerated Dose

The algorithm for determining the MTD is as follows:

- Up to six subjects and two controls will be enrolled at each dose level constituting each cohort. Subjects will be evaluated for four hours after receiving the last of the three doses and again at discharge from the hospital or one week later, whichever is sooner.
- DLT is previously defined in [Section 5.3.2](#).
- If no DLTs are observed in a patient at Post-Dose #3 of DDFPe or placebo the Medical Monitor may allow progression to the next patient.

- After all 8 subjects have been enrolled in a cohort, the Medical Monitor will review the data. A decision as to whether the study may proceed to the next cohort will be made.
- If a total of two or fewer subjects in an 8 subject cohort experience a DLT, escalation to the next cohort may proceed if approved by the Medical Monitor. If three or more DLTs were observed, the Medical Monitor may consult with the Research Pharmacist to determine if the observed DLTs occurred in subjects who received DDFPe or placebo. If any of the DLTs were observed in the subjects receiving placebo, the Medical Monitor may allow the study to proceed as long as two or fewer subjects with DLTs received DDFPe.
- If three or more subjects who received DDFPe in an 8 subject cohort experience a DLT, the MTD will be determined to have been exceeded and further enrollment in the cohort as well as dose escalation will stop. The dose administered to the previous cohort will be considered to be the MTD.
- Subjects who withdraw from the study for reasons other than a DLT may be replaced.
- The Medical Monitor will review all safety data for each patient and cohort and must grant approval before proceeding to the next patient and/or cohort.
- Exploration of lower dose levels intermediate to a level previously shown to be well tolerated may be considered. In addition to reducing the dose, this might include reducing the number of doses, increasing the time between doses, and/or altering the infusion time.
- The dose exploration will be complete when either: (1) the MTD has been defined or (2) when no MTD has been reached but six subjects and two controls have been treated at the last cohort level approved by the Medical Monitor.

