5.3.2 Dose Limiting Toxicity

Dose limiting toxicity (DLT) will be defined by the following criteria:

- Clinically significant changes in vital signs:
 - Heart rate \pm 50% from baseline
 - Respiratory rate >30 /min
 - Systolic blood pressure < 90 mmHg or >220 mmHg
 - Diastolic blood pressure >110 mmHg
- New (i.e. not seen at baseline) ECG changes consistent with:
 - Acute right ventricular dilation or strain
 - Incomplete or complete bundle branch block
 - Q waves in leads III and aVF
 - T-wave inversion and/or ST segment changes in the precordial leads
 - Any other clinically significant cardiac arrhythmia
- Common Terminology Criteria for Adverse Events (CTCAE) 4 Grade 3 or higher cough, dyspnea, chest pain-cardiac or non-cardiac, chest wall pain or hypoxia (See [Appendix 1](#) for specific criteria)
- NIHSS: sudden worsening of 4 or more from the baseline (pre-DDFPe initiation)
- The Medical Monitor will review all data collected at Post-Dose #3 (approximately 4-6 hours after the end of the Dose #3 infusion of DDFPe or placebo for each subject). Enrollment will be on hold until the Medical Monitor has reviewed the data and approves enrollment of an additional subject. The Medical Monitor may choose to temporarily halt the study if serious concerns arise regarding subject safety.

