7.5.8 ECG

A 12-lead ECG will be performed as part of the Screening process to assure that subjects with serious arrhythmias are appropriately excluded from the study. The ECG will be inspected by the treating physician and the investigator. If a serious rhythm disturbance is observed, a cardiologist may be consulted to confirm the findings. If confirmed by the cardiologist, the subject will be withdrawn from the study prior to administration of DDFPe. After the study is completed, all ECGs will be reviewed by a board certified cardiologist to confirm that no new arrhythmias developed during the course of treatment.

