8.5 Medical Monitor

A Medical Monitor (MM) will be selected. The MM will be a licensed physician who is familiar with cardiovascular disease and stroke. The MM will review the data collected after each patient and after each dose level and will provide an opinion to the investigator as to whether it is advisable to proceed with dose escalation as described in Section 5.3.3. As part of the review, the MM will review all AEs and assure that any SAEs have been reported appropriately.

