10.2 Clinical Data

Demographic data will be presented as the mean \pm SD (range) for normally distributed data (median \pm interquartile range for non-normal data).

Clinical data includes vital signs and pulse oximetry (pre- and post-intervention). Pre- and post-intervention data will be grouped and examined for differences using a two-sided t-test or ANOVA, as appropriate. Pre- and post- laboratory data will be compared in a similar manner. ECGs will be read by a board-certified cardiologist and clinically significant changes will be described.

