Appendix 4: Schedule of Time and Events

	Day 1					Day 4	Day 7±1 or Day of Discharge	Day 30 ±7	Day 90 ±14
Study Procedures	Screening (Baseline)	Dose #1 ^a	Dose #2 ^a	Dose #3 ^a	Post- Dose #3 ^b				
Informed Consent	X								
I/E Criteria	X								
Concomitant Meds	X	X	X	X	X				
Medical History ^c	X						X	X	X
Physical Exam ^c	X				X		X	X	
Weight	X								
Vital Signs ^d	X	X	X	X	X		X	X	
Pulse Oximetry ^e	X	X	X	X	X		X		
Modified Rankin Scale	X						X	X	X
NIHSS	X		X ^f	X ^f	X		X	X	
ECG ^g	X				X		X		
Pregnancy Test ^h	X								
Lab Studies ⁱ	X				X		X		
Administer DDFPe ^j		X	X	X					
Adverse Events		X	X	X	X	X	X	X	X

a Each dose of DDFPe or placebo is to be administered intravenously over 5-10 minutes. Start and stop times will be recorded as will the volume infused.

b Post-dose #3 concludes approximately 4-6 hours after the end of the Dose #3 infusion.

c Brief, targeted medical history and physical exam.

d Vital signs (blood pressure, heart rate, respiratory rate) will be done every 15 minutes through the end of Post-Dose #3 (approximately 4-6 hours) and then consistent with standard procedures for the hospital unit. Temperature will be done every 1-4 hours consistent with the hospital unit standard procedures.

e Continuous or spot readings may be taken; if continuous readings are used, record the measurement every 15 minutes.

f To be performed within 60 minutes following the dose.

g 12-lead ECG to be examined at the bedside by the study personnel and later reviewed by a board certified cardiologist.

h Serum pregnancy test will be done in pre-menopausal women.

i To include: CBC, electrolytes (Na, K, Cl), BUN, creatinine, LFTs, calcium, albumin, glucose

j DDFPe or placebo to be administered over 5-10 minutes intravenously through a peripheral or central IV. The interval between the end of one dose and the beginning of the next should be 90 ± 10 minutes.

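### New ECG changes count as DLTs, but the planned cardiologist read comes after the study, too late for either escalation, and no section says which read decides a DLT

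*Combined protocol and SAP*

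**What the plan says.** **DLT definition.** Section 5.3.2 lists five items under "New (i.e. not seen at baseline) ECG changes consistent with": right ventricular dilation or strain, bundle branch block, inferior Q waves, precordial T-wave or ST changes, and any other clinically significant arrhythmia.

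**Reads available before escalation.** Appendix 4, footnote g, has the tracing "12-lead ECG to be examined at the bedside by the study personnel and later reviewed by a board certified cardiologist". Section 5.3.2 adds that "The Medical Monitor will review all data collected at Post-Dose #3", and section 7.6 includes an ECG in those data. Section 8.5 describes the reviewer: "The MM will be a licensed physician who is familiar with cardiovascular disease and stroke". Section 5.3.3 makes approval a condition: "The Medical Monitor will review all safety data for each patient and cohort and must grant approval before proceeding".

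**Cohort decision.** Section 5.3.3 says: "After all 8 subjects have been enrolled in a cohort, the Medical Monitor will review the data". Three or more DDFPe subjects with a DLT mean that the MTD was exceeded and that the previous level is the MTD.

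**Specialist read.** Section 7.5.8 says: "After the study is completed, all ECGs will be reviewed by a board certified cardiologist to confirm that no new arrhythmias developed". Section 10.2 gives no timing: "ECGs will be read by a board-certified cardiologist and clinically significant changes will be described". The cardiologist consultation mentioned earlier in 7.5.8 concerns screening only.

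**Later evaluation.** Section 5.3.3 also lists an evaluation at discharge or one week. Section 7.8 shows that it includes an ECG.

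**The concern.** The MTD is the primary objective, and section 10.3 derives it from the DLTs. The protocol plans a specialist read of every tracing, yet times it so that it cannot inform either escalation. No section says which read determines a DLT when the early and specialist reads disagree.

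This leaves two possible readings, and neither is satisfactory:

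- **The late read counts.** It could turn 2 of 6 into 3 of 6 at a level after the next cohort has been treated above it. It could also turn 3 of 6 into 2 of 6 after escalation has stopped. The protocol has no rule for either case.
- **The late read does not count.** The only planned specialist assessment of a DLT criterion then never enters the MTD determination.

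**Working it through.** **1. Structure (sections 3.1 and 5.3.3).** 3 levels × (6 DDFPe + 2 placebo) = 24 subjects, matching the Study Summary. Three levels give 3 − 1 = 2 escalations. Section 10.1 states no sample size calculation, so the plan has no operating characteristic to reproduce.

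**2. Order of events.** For each cohort the sequence is: screening ECG; Post-Dose #3 ECG, read at the bedside; Monitor review and enrolment hold after each subject; cohort review after the eighth subject; escalation. The cardiologist's read under 7.5.8 follows the end of the study, and so follows both escalations. *Later* in footnote g does not bring it forward.

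**3. Size.** The documents give no DLT rate and no ECG misreading rate, so both are assumed. Let p be the per-subject probability of a DLT recognised before the cohort review. Let r be the probability that a subject with no other DLT has an ECG DLT missed by both the bedside read and the Monitor. The full rate is then

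p′ = p + (1 − p)·r

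Escalation needs at most 2 DLTs among the 6 DDFPe subjects. The excess of cohorts escalated is

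P(Bin(6, p) ≤ 2) − P(Bin(6, p′) ≤ 2)

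| p | P(≤2 of 6) | p′, r = 1% | Excess, points | p′, r = 2% | Excess, points |
|---|---|---|---|---|---|
| 0.05 | 99.78% | 0.0595 | 0.14 | 0.069 | 0.34 |
| 0.10 | 98.42% | 0.109 | 0.42 | 0.118 | 0.91 |
| 0.20 | 90.11% | 0.208 | 1.01 | 0.216 | 2.06 |
| 0.30 | 74.43% | 0.307 | 1.31 | 0.314 | 2.63 |
| 0.40 | 54.43% | 0.406 | 1.24 | 0.412 | 2.49 |

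Example: for p = 0.30 and r = 2%, p′ = 0.30 + 0.70 × 0.02 = 0.314, and 74.43% − 71.80% = 2.63 points.

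The range is 0.1 to 2.6 points. The calculation treats subjects as independent and treats 2 or fewer DLTs as automatic escalation. Section 5.3.3 only permits escalation if the Monitor approves, so the real effect could be smaller.

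**4. Over-calls.** If misses and over-calls are equally common at 2% each, 0.3 to 2.5 points of cohorts escalate that the final count would stop, and the same share stops that it would escalate. The net is about zero, but each is a decision that the final count would reverse.

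**5. Discharge/Day 7 evaluation.** The cohort review is placed after eight subjects are enrolled (5.3.3), at the end of each cohort (7.2), after its completion (8.4) and after each dose level (8.5). None of these sections, nor 5.3.2, says whether the discharge/Day 7 evaluation must be in hand at that review, or whether findings there count as DLTs.

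**The case against.** The strongest reply is that the design is legitimate: physicians review in real time and a specialist confirms afterwards. The Monitor knows cardiovascular disease, sees every Post-Dose #3 ECG and must approve each step. Section 10.3 refers back to 5.3.3, where the Monitor decides, and 7.5.8 describes the cardiologist's role as confirmation. On that reading the Monitor's count governs and nothing is reversed.

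Much of this stands. ECG DLTs can be recognised before escalation, and no section says that the late read revises a DLT count. But no section says that it does not, and leaving the only specialist read out of both decisions gains nothing beyond a single batch of reading.

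Three stronger inferences are tempting, but the documents do not support them:

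- **That the sections name different cohort review points.** *Completion* and *end* are near-synonyms. The hold in 5.3.2 and the approval requirement in 5.3.3 already mean that the eighth subject's Post-Dose #3 data are reviewed before escalation. Only the status of the discharge/Day 7 evaluation is open.
- **That the cardiologist would look only for arrhythmias.** Section 10.2 already has the cardiologist's read yield clinically significant changes. Section 5.3.2 closes its ECG list with any *other* arrhythmia, which suggests that the protocol uses the word loosely.
- **That a subject would usually be dosed at the next level before the last discharge/Day 7 examination.** With 24 subjects over 18 months (or 15, allowing for 90-day follow-up) and Poisson arrivals (assumed), the mean gap is 22.8 (or 19.0) days. Expected arrivals in 8 days are 8/22.8 = 0.35 (or 8/19.0 = 0.42). The chance of none is about 70% (or 66%), so the usual number is zero.

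**Conclusion.** The point holds as a minor one. As section 7.5.8 is written, neither escalation can use the cardiologist's read, and the protocol does not name the read that determines an ECG DLT. The documents do not support saying that escalation proceeds without ECG review, or that the end-of-study read will overturn the MTD.

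The expected effect is small: about 0.1 to 2.6 percentage points of cohorts, under an assumed joint miss rate of 1% to 2% and assumed DLT rates of 5% to 40%. The case for acting is that one reclassified tracing can decide a level at the threshold of three in six, and that the correction uses a read already planned.

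The status of the discharge/Day 7 evaluation is secondary. It needs reconciliation only.

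**What to change.** 1. Amend 7.5.8 and Appendix 4, footnote g, so that the planned cardiologist read covers each cohort's ECGs available at the cohort review, is completed before that review, and is made against the ECG criteria in 5.3.2. This means at least the screening and Post-Dose #3 tracings: 2 × 8 = 16 per cohort, and 2 × 16 = 32 before the two escalations. Discharge/Day 7 tracings not yet available can be read with a later batch, so this change does not fix the time point left open in item 3.
2. State which read is used for the DLT count when the bedside, Monitor and cardiologist reads differ.
3. Reconcile 5.3.2, 5.3.3, 7.2, 8.4 and 8.5 on whether the discharge/Day 7 evaluation must be in hand at the cohort review and whether findings there count as DLTs. The time point is for the sponsor to choose.

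**Cost.** No added test, visit or reader. The same reads are done in three batches instead of one, with a short turnaround before each of the two escalations. Items 2 and 3 are wording changes.

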5.6.3 Criteria for Stopping the Investigational Product

The investigational agent will be discontinued in the event that:

- Life-threatening disease progression occurs
- Unacceptable adverse events
- Subject wishes to withdraw from the study
- Changes in the patient's condition that, in the opinion of the investigator, present unacceptable risk to the subject

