6.4 Withdrawal Criteria

Subjects may choose to withdraw from the study at any time for any reason. Additionally, the investigator may choose to remove subjects from the study. Any subject withdrawing their consent to participate in the study or their authorization to use their protected health information will be withdrawn from the study.

Subjects will be informed that the investigational product may be discontinued by the investigator even if the subject and/or the LAR wish to continue. This may occur for the following reasons:

- Serious Adverse Event (SAE) believed to be related to investigational product
- Intolerable side effects
- Failure to complete required study procedures
- Clinically significant laboratory or ECG abnormalities
- Significant change in oxygenation as measured by pulse oximetry
- Initiation of treatment with a prohibited drug during the intervention phase
- Non-compliance with the treatment regimen

Subjects may also be withdrawn for any reason if the investigator believes that it is in the best interest of the subject to discontinue the study.

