8.6 Risks and Benefits

Risks may include pain from IV placement, hypotension, reversible inflammatory changes in the lungs, nausea, vomiting, drowsiness, dizziness, fever, headache, reduced or elevated blood pressure, blanching of the gums, and allergy to soy or eggs. There may be unanticipated adverse events or outcomes. It is anticipated that oxygen delivery to ischemic areas of the brain may improve thereby changing clinical signs. It is unclear as to whether this might result in reduced cerebral tissue loss or any improvement in outcome following stroke. There may be no benefit to subjects.

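### The DLT list behind the MTD count omits drug-related harm for which other sections stop treatment, and no section says how such cases are counted

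*Combined protocol and SAP*

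**What the plan says.** Section 5.3.3 holds the rule that answers the primary objective. It declares the MTD exceeded when three or more DDFPe subjects in an eight-subject cohort have a DLT. On what a DLT is, it says only "DLT is previously defined in" Section 5.3.2.

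Section 5.3.2 opens with "Dose limiting toxicity (DLT) will be defined by the following criteria" and then names four kinds of event: limits on heart rate, respiratory rate and blood pressure; new ECG changes; CTCAE "Grade 3 or higher cough, dyspnea, chest pain-cardiac or non-cardiac, chest wall pain or hypoxia"; and an NIHSS worsening of 4 or more from baseline. Its one open-ended entry is confined to arrhythmia. Its last bullet describes the Medical Monitor's review and is not a criterion.

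Other sections reach further:

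- The synopsis (Primary Outcome Measures) describes DLT as also including clinically significant changes in pulse oximetry, clinical symptoms and laboratory values.
- 5.6.3 discontinues the product for "Unacceptable adverse events".
- 6.4 lets the investigator discontinue it for "Serious Adverse Event (SAE) believed to be related to investigational product", for intolerable side effects, for clinically significant laboratory or ECG abnormalities, and for a significant change in oxygenation.
- 8.6 names among the risks "reversible inflammatory changes in the lungs, nausea, vomiting, drowsiness, dizziness, fever, headache".

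There are two replacement rules. 5.3.3 says "Subjects who withdraw from the study for reasons other than a DLT may be replaced". 6.5 lets the investigator replace anyone who leaves or is removed before the Day 7 visit is completed, and makes no exception for a DLT.

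**The concern.** A maximum tolerated dose should reflect who tolerated the dose. Here the events that end treatment for intolerance and the events that count towards the MTD are defined in different sections, and nothing links them. A DDFPe subject stopped after Dose 1 or 2 for drug-related harm outside the 5.3.2 list did not tolerate the three-dose regimen named in 2.1, yet adds nothing to the count of three. With six DDFPe subjects per dose, one or two such cases can reverse the formal result. The synopsis and 5.3.2 also give two different accounts of the primary outcome, so two analysts could score the same cohort differently.

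**Working it through.** **1. The passages side by side**

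| Event | In the 5.3.2 list? | Elsewhere | Status in the MTD count |
|---|---|---|---|
| Related SAE during dosing | Only if it also meets a listed sign | 6.4: product may be stopped | None stated |
| Related SAE after Dose 3 | Only if it also meets a listed sign | No dose is left to stop | None stated |
| Unacceptable or intolerable adverse event | Only if it also meets a listed sign | 5.6.3 and 6.4: stops product | None stated |
| Laboratory abnormality | No | Synopsis: part of DLT; 6.4: product may be stopped | Synopsis and 5.3.2 disagree |
| Oxygenation change short of Grade 3 hypoxia | No | Synopsis: part of DLT; 6.4: product may be stopped | Synopsis and 5.3.2 disagree |

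**2. What happens to such a subject under 5.3.3**

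- Taken off drug and kept in follow-up: occupies one of the six DDFPe places and scores as DLT-free.
- Withdrawn from the study: the reason is not a DLT, so replacement is allowed and the subject can leave the six.

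**3. The plan's own figure.** 3 dose levels × (6 DDFPe + 2 placebo) = 24, which matches the synopsis. Section 10.1 says that no sample size estimate was made. There is no target DLT rate or stopping probability to reproduce.

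**4. Effect on the count.** Let a be the rate of listed DLTs and b the rate of off-list intolerance, mutually exclusive. Both are assumptions. The chance that the count reaches three is P(X ≥ 3) for X binomial with n = 6 and:

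- kept and uncounted: p = a
- all replaced: p = a/(1 − b), because each of the six places ends with a subject who is not an off-list case
- counted: p = a + b

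For a = b = 0.20:

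- p = 0.20: 1 − (0.2621 + 0.3932 + 0.2458) = 0.099
- p = 0.20/0.80 = 0.25: 1 − (0.1780 + 0.3560 + 0.2966) = 0.169
- p = 0.40: 1 − (0.0467 + 0.1866 + 0.3110) = 0.456

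| a | b | Kept, uncounted | Replaced | Counted |
|---|---|---|---|---|
| 0.10 | 0.10 | 1.6% | 2.1% | 9.9% |
| 0.10 | 0.20 | 1.6% | 2.9% | 25.6% |
| 0.20 | 0.20 | 9.9% | 16.9% | 45.6% |

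In every row replacement gives a higher figure than keeping the subject uncounted. The loss therefore comes from the definition, and changing only the replacement sentence would not repair it.

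**5. A concrete cohort.** Suppose two DDFPe subjects have listed DLTs and two are stopped for off-list drug-related harm. If the latter are kept, 4 of 6 did not tolerate the dose and the rule reads 2 of 6. If they are replaced, 4 of 8 dosed did not tolerate it and the rule again reads 2 of 6. Either way the count leaves escalation open, subject to the Medical Monitor's approval.

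**The case against.** The strongest reply is that the count does not act alone. Under 5.3.2 and 5.3.3 enrollment is held after every subject until the Medical Monitor approves the next. 8.4 also requires moderate or severe signals that are unanticipated and probably or definitely related to be discussed with the sponsor and the manufacturer before further enrollment. All adverse events are recorded and reported. This stands: the percentages above describe the formal count, not the chance that the study would in fact continue. But the review can halt the study without altering the count that declares the MTD exceeded, and the 8.4 discussion does not plainly cover risks already named in 8.6.

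Second, many serious reactions would trip a listed sign, such as low systolic pressure, Grade 3 hypoxia or NIHSS worsening, with vital signs recorded every 15 minutes. That narrows the gap. It does not close it for laboratory toxicity or for general symptoms without those signs. Allergy is a weak example: 8.6 names only soy and egg allergy, and 6.3.13 excludes subjects with it.

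Third, a reader might infer that replacement is how intolerance disappears. The documents do not support that. The quoted sentence concerns leaving the study, whereas 5.6.3 and the list in 6.4 concern stopping the product (though 6.4 carries a withdrawal heading), and replacement is optional. The figures also show it to be the lesser effect.

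Fourth, a reader might infer that these events are definitely not DLTs, or that a halt by the Medical Monitor leaves the trial without an end. The synopsis wording could take in several of them, so the first is an unresolved inconsistency. As to the second, 5.3.3 provides for completion with no MTD reached, at the last cohort level the Medical Monitor approved, and allows intermediate dose levels to be explored.

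**Conclusion.** The point holds as an inconsistency in the definition of the primary outcome. The only DLT definition that 5.3.3 uses is narrower than the synopsis and is not linked to the tolerability stops in 5.6.3 and 6.4. Followed literally, off-list drug-related intolerance is scored DLT-free or may be replaced, and 6.5 conflicts with 5.3.3 on whether a subject with a DLT can be replaced.

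The size depends on rates that the documents do not give. Over the assumed pairs, the chance that the count reaches three runs from 1.6% to 9.9% with such cases kept uncounted, from 2.1% to 16.9% with all of them replaced, and from 9.9% to 45.6% with all of them counted. This assumes independent subjects, listed and off-list events that do not overlap, and six evaluated DDFPe subjects. Overlap with listed signs would shrink the difference. The documents do not show that an intolerable dose would be cleared in practice, because the Medical Monitor can refuse each step.

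**What to change.** Reconcile the synopsis, 5.3.2, 5.3.3, 5.6.3, 6.4 and 6.5 so that one DLT definition drives the count. That definition should state explicitly how two groups enter the MTD count: related SAEs, including those arising after Dose 3 when no dosing remains to be stopped, and discontinuations for drug-related intolerance. Which events qualify, and at what degree of relatedness, is clinical content for the sponsor to decide.

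Align the replacement rules in 5.3.3 and 6.5 so that a subject removed for tolerability reasons stays in the cohort's evaluation, and settle whether a subject with a DLT can be replaced. The criteria for stopping product need not change for this purpose; only their status in the count does.

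The cost is an amendment touching several short passages. If such events are counted, escalation may stop more often, possibly materially, as the figures show. Attribution made blind may count some placebo events; the existing step in 5.3.3, in which the Medical Monitor may ask the Research Pharmacist which treatment was given, deals with those. Relatedness also brings judgement into a list that now rests mostly on measured or graded criteria, so whoever makes that judgement should be named in advance.
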